### Introduction

AAA is an asymptomatic widening of the infrarenal aortic diameter to  $\geq 3$  cm. Male sex, increasing age, and heredity are important non-modifiable risk factors for development of the disease. This multifactorial disease has life-threatening consequences; if rupture occurs, mortality is 100 % if left untreated. The risk for rupture is closely related to the size of the AAA, and identification of patients with smaller AAA is therefore crucial. Fewer women than men in the population have AAA (1:5) but women diagnosed with AAA suffer a higher aneurysm growth rate, higher rupture risk, higher complication rate when treated, and have a more challenging aneurysm anatomy. Women are not included in any national screening program.

In 2016 the Swedish National Board of Health and Welfare (NBHW) published guidelines recommending population based screening of 65-year old men, based on a reported 40% reduction in aneurysm-related death in screened men. We have recently reported on the 4% annual decline in aneurysm mortality in invited men. The incremental cost-efficiency ratio was 8000 Euro/QALY. (Circulation, Wanhainen, 2016).

### Family History – and Gender Aspects.

We have, as others, reported on the high hereditary risk for AAA, but no systematic screening targeting FDR of AAA patients is presently performed although recommended in international guidelines. We have tested a nurse-based active detection route in three Swedish Vascular Departments to invites siblings to be screened, and succeed with a participation rate of 80%, and prevalence rate of 10% in them.

In a local FDR screening program performed in 2012 in our institution, less than 10% of siblings had been screened before our invitation. It is highly probable that the adult offspring of AAA patients have an even lower awareness due to younger age at the probands onset of disease, and lower participation in the care of diseased relatives for younger next-of-kin.

**Genetic Associations.** In a twin study from our group: 172,890 twins registered at the time of the study, gave a study base of 265 twins (81% men; mean age 72 years; range, 48-94) with AAA. In the structural equation models, genetic effects accounted for 70% (95% CI 0.33-0.83), nonshared environmental effects for 30% (95% CI 0.17-0.46). Concordances and correlations were higher in MZ compared with DZ twins, indicating genetic effects.

### Study Objectives and Endpoints

**Aim: Primary aim.** To investigate the prevalence of AAA in adult offsprings to AAA patients compared to controls, stratified by sex

**Hypothesis** The prevalence of AAA in adult offsprings to AAA patients is 4-fold higher than in persons in the population.

**Secondary aim.** To investigate the awareness of the hereditability for AAA in adult offspring to AAA patients compared to controls, including anxiety levels.

**Hypothesis** The adult offspring to AAA patients have a low awareness of AAA risk, but higher than persons in the population.

**The third aim** is to evaluate the cost efficiency of the program, compared to sibling screening and screening in 65-year old men.

[figure not shown]
**Hypothesis** The selective registry-based screening in adult offsprings to AAA patients is as cost-efficient in detection of persons at risk as the program for 65-year old men.

**Fourth Aim.** To evaluate the registrybased detetion model- an evaluation of the feasibility.

**Hypothesis** The selective registry-based screening can be effective and work in a national setting.

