### Estimated Sample Size “Power analysis”

**Aim: Primary aim.** To investigate the prevalence of AAA in adult offspring to AAA patients compared to controls. **Hypothesis** The prevalence of AAA in adult offspring to AAA patients is higher than in persons in the population.

**Power analysis.** We estimate the participation rate to be lower than in the population-based screening (80%) due to lower age in invited adult offspring ; approximately 65%. Therefore an additional 200 women and 180 men will be invited, in order to obtain the examined persons below.

MEN: POWER: Alfa 0.05; power 0.80; estimated prevalence 7 % in offspring, 1.0% in controls; minimum of 166 persons in each group is requested. (men). 65% participation.

Invitation: 100 persons more: **350 invited men in offspring and 350 in control group**

WOMEN: POWER: Alfa 0.05; power 0.80; estimated prevalence 5 % in offspring, 0.5% in controls; minimum of 206 persons in each group is requested. 65% participation.

Invitation: 100 persons more: **400 women in offspring and 400 in control group.**

Table 1. Study assessments.

Visit	Baseline
Time window	At US
Informed consent	X

Demographic data	X
Medical history and clinical examination	X
Concomitant medication	X
US Aortic diameter	X
Questionnaires	X
Cases referred to vascular center	

aAge, sex, civil status, education level. b Current medical conditions and medical history, blood pressure, ankle-brachial index, pulse, height and weight. c Creatinine (mmol/L). d HADS and EQ-5D and self reported knowledge of AAA risks.

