### General Analysis Considerations

Final analyses will be performed when lowest possible number of participants have been examined.

Continuous checks on participation is performed according to power calculation.

Invitations are however sent two weeks before examination.

All data will be deidentified and transferred to an SPSS file for statistical analysis.

The Adult offspring or control, women and men will be presented separately. Missing cases, non-participants will be presented. Index persons, their parents with AAA will be presented with sex and age at AAA diagnosis.

Multiple imputations or random effects models will not be used.

Per protocol analysis will be performed, based on the four groups; sex (2) and heredity (yes/no).

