### Summary of Study Data

All continuous variables will be summarized using the following descriptive statistics: n (non-missing sample size), mean and standard deviation. The frequency and percentages (based on the non-missing sample size) of observed levels will be reported for all categorical measures. In general, all data will be listed, sorted by groups and stratified by sex. All summary tables will be structured with a column for each group (Adult offspring or control, women and men). Primary endpoint; prevalence will be presented for each strata and group. They will be presented also for age groups.

Demographic variables, concurrent illnesses and baseline variables are outlined as usual. Their apprehension of their risk for disease will be presented for the four groups also including their data on the index person.

Derived variables to be included in the analyses are the subscales of the HADS instrument, HADS-Anxiety (HADS-A) and HADS-Depression (HADS-D) as well as the subscales of the EQ-5D.

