### Efficacy Analyses

$\chi^2$  test will be used to analyse categorical variables and independent *t* test to analyse continuous data. For comparisons of independent groups, Student's *t* test will be used for normally distributed data, and Mann-Whitney for non-parametric data or small samples. Categorical data will be analysed by Fischer's test where possible. Continuous variables are presented as means (SD), categorical variables are presented as counts and proportions as appropriate.

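### The primary hypothesis is a 4-fold prevalence, but the sample size rests on 7-fold in men and 10-fold in women, so the stated 80% power does not belong to it

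*Combined protocol and SAP*

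**What the plan says.** The Study Objectives and Endpoints section gives the primary aim as "To investigate the prevalence of AAA in adult offsprings to AAA patients compared to controls, stratified by sex". The hypothesis directly below it is "The prevalence of AAA in adult offsprings to AAA patients is 4-fold higher than in persons in the population".

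The sample size section repeats the hypothesis without a fold size: "The prevalence of AAA in adult offspring to AAA patients is higher than in persons in the population". It then sizes each sex separately at alpha 0.05 and power 0.80. For men: "estimated prevalence 7 % in offspring, 1.0% in controls; minimum of 166 persons in each group is requested". For women: "estimated prevalence 5 % in offspring, 0.5% in controls; minimum of 206 persons in each group is requested". At about 65% participation it invites 350 men and 400 women per group.

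Three further statements bear on the point:

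- General Analysis Considerations, on timing: "Final analyses will be performed when lowest possible number of participants have been examined".
- Summary of Study Data, on the primary endpoint: "Primary endpoint; prevalence will be presented for each strata and group".
- Efficacy Analyses, which names the chi-square test and adds: "Categorical data will be analysed by Fischer's test where possible".

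**The concern.** The rates used for sizing give ratios of 7/1.0 = 7 in men and 5/0.5 = 10 in women. Neither is 4, nor 5 if the wording is read as four times more on top of the control rate. The plan's only power figure therefore belongs to a larger effect than the one named as the primary hypothesis, and no power is given for the named one.

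Both directions of misreading are at stake. A non-significant result, especially in women, could be taken as evidence against a 4-fold excess when the study had little chance of detecting one. A significant result could be reported as confirming 4-fold, although a test of equality cannot show that and the plan specifies no interval for the ratio.

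**Working it through.** **Inputs.** From the sample size section: alpha 0.05, power 0.80, the two pairs of rates, 166 and 206 per group, 65% participation, and 350 and 400 invited per group. From Study Objectives: 4-fold. Expected yield per group is 0.65 × 350 = 227.5 men and 0.65 × 400 = 260 women. The minimum sizes are one reading of the vague rule for when the final analysis takes place, so both sizes are shown.

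**Step 1: reproduce the plan's figures.** The plan states neither formula nor sidedness. The two-sided pooled formula, with p̄ the mean of p1 and p2, is

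n = [1.960·√(2p̄(1−p̄)) + 0.842·√(p1(1−p1)+p2(1−p2))]² / (p1−p2)²

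- Men, 0.07 and 0.01: (0.5432 + 0.2305)² / 0.06² = 166.3, against 166 printed.
- Women, 0.05 and 0.005: (0.4533 + 0.1928)² / 0.045² = 206.1, against 206 printed.

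The sizing arithmetic is therefore sound. Close alternatives are two-sided unpooled (163.5 and 203.4) and one-sided with continuity correction (163 and 205), so the two-sided pooled form is an inference.

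**Step 2: power at a ratio of 4.** The plan does not say which rate the fold is anchored to, so each is held in turn.

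Power = Φ{[(p1−p2)√n − 1.960·√(2p̄(1−p̄))] / √(p1(1−p1)+p2(1−p2))}

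Example, men with the control rate held (4% against 1%), n = 166: (0.03 × 12.884 − 0.4327) / 0.2198 = −0.21, and Φ(−0.21) = 42%.

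| Ratio of 4 | Rates | Minimum size | Expected yield | n per group for 80% |
|---|---|---|---|---|
| Men, control held | 4% vs 1% | 42% | 54% | 424 |
| Men, offspring held | 7% vs 1.75% | 65% | 78% | 238 |
| Women, control held | 2% vs 0.5% | 28% | 34% | 861 |
| Women, offspring held | 5% vs 1.25% | 59% | 69% | 337 |

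**Step 3: a ratio of 5.** Men/women with control rates held: 57%/39% at the minimum size and 71%/47% at the expected yield. With offspring rates held: 72%/66% and 85%/76%. Exact power of the uncorrected chi-square test for that last pair is 88%/81%.

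**Step 4: exact power of the named tests.** At a ratio of 4, the best case for men (offspring rate held, 227 per group) is 81% by chi-square and 75% by Fisher. The same case for women (260 per group) is 73% and 63%. Fisher's test already falls to 76%/77% at the sizing rates and minimum size, so part of its shortfall comes from the test. Moving to a ratio of 4 with Fisher throughout takes it to 27%/11% (control held) or 56%/49% (offspring held).

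**Step 5: what a significant result would show.** Score 95% intervals for the prevalence ratio:

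- 12 vs 2 of 166 men: 1.5 to 23.7.
- 10 vs 1 of 206 women: 1.7 to 60.4.

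Enumeration over the sizing rates and both ratio-of-4 scenarios, at both sizes, shows that 83% to nearly 100% of significant results have an interval containing both 4 and the sizing ratio. Exceptions exist: 20 vs 8 of 227 gives 1.15 to 5.46, and 16 vs 0 of 166 has a lower limit of 4.24. Zero control cases are a real prospect at the sizing rates and minimum sizes: 0.99^166 = 19% in men and 0.995^206 = 36% in women.

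**The case against.** The strongest reply is that the power analysis is coherent in itself. It states the hypothesis as higher, uses the plan's best estimates of prevalence, and is matched by tests of equality. On that view the stray item is the 4-fold wording, and the study is not underpowered for what it tests. This stands in part: it is a good reason to reconcile the wording and not to enlarge the study. It does not remove the conflict, because the 4-fold statement is the declared primary hypothesis.

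Second, the hypothesis sentence does not itself mention sex. With the sexes combined, power at a ratio of 4 would be 60% (control held) or 89% (offspring held) at the minimum sizes, and 73% or 96% at the expected yield. But the aim directly above is stratified by sex, sizing and analysis are by sex, and no combined analysis is planned.

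Third, the low ends of the ranges replace the plan's own offspring estimates with 4% and 2%. That is true, and it is why both anchors are shown. The high ends likewise replace its control rates.

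Fourth, over-invitation helps. For men it brings the most favourable ratio-of-4 case to about 80%. For women it does not: no ratio-of-4 case passes 73%.

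Fifth, sidedness is not settled. One-sided with continuity correction, ratio-of-4 power at the minimum sizes is about 40% to 67% in men and 24% to 60% in women, which changes nothing material.

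**Conclusion.** The concern holds, as an inconsistency between two parts of the plan and not as a calculation error. The stated 80% applies to 7-fold and 10-fold differences and not to the 4-fold primary hypothesis.

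Analysed by sex at a ratio of 4, women stay below 80% in every case computed. Men come to about 80% only with the offspring rate held and the full expected yield achieved. If a ratio of 5 is meant, the most favourable case does reach 80%. The figures assume a two-sided 0.05 test, equal groups, the pooled formula unless stated, and one of the plan's two rates held fixed.

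Separately, a significant p-value would not establish 4-fold, and the interval would usually be too wide to tell it from the sizing ratio. This should be fixed, but it does not invalidate the study.

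**What to change.** 1. Reconcile the Study Objectives and sample size sections in one of two ways.
   - State the primary hypothesis with the sex-specific prevalences used for sizing: 7% against 1.0% in men and 5% against 0.5% in women.
   - Or keep 4-fold, say whether it means a ratio of 4 or 5 and which rate anchors it, and add to the sample size section, for a ratio of 4: *At 166 men and 206 women per group, 80% power applies to 7% vs 1.0% and 5% vs 0.5%. For a prevalence ratio of 4, power in men/women is about 42%/28% with control rates held or 65%/59% with offspring rates held; at the expected yield it is about 54%/34% or 78%/69%.* For a ratio of 5, use the Step 3 figures instead.
2. State the sample size formula and whether the test is two-sided.
3. In Efficacy Analyses, add the sex-specific prevalence difference and ratio with 95% score or exact intervals that remain valid with zero control cases. Say that the fold statement will be judged from the interval and not from the p-value.

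The cost is a few sentences and one reporting line. Sample size and planned tests stay as they are. The one drawback is that the disclosed power at 4-fold looks less favourable than 80%.

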## Study Methods

**Study Design.** Population based case-control point-prevalence study.

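### The primary hypothesis is stated as 4-fold in one section and as higher in another, and no planned analysis estimates the ratio or its uncertainty

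*Combined protocol and SAP*

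**What the plan says.** All references are to the combined protocol and SAP.

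- Under Study Objectives and Endpoints, the primary aim is to compare the prevalence of AAA in adult offspring with that in controls, by sex. Its hypothesis is a statement of size: "The prevalence of AAA in adult offsprings to AAA patients is 4-fold higher than in persons in the population".
- Under Estimated Sample Size, the hypothesis attached to the same aim gives a direction only: "The prevalence of AAA in adult offspring to AAA patients is higher than in persons in the population". The sizing inputs for men are "estimated prevalence 7 % in offspring, 1.0% in controls; minimum of 166 persons in each group is requested" and for women "estimated prevalence 5 % in offspring, 0.5% in controls; minimum of 206 persons in each group is requested". These imply ratios of 7 and 10, not 4.
- Summary of Study Data presents the primary endpoint as a prevalence per group and stratum.
- Efficacy Analyses names the chi-square test for categorical variables and adds "Categorical data will be analysed by Fischer's test where possible". Results are shown as counts and proportions.
- Reporting Conventions mentions regression coefficients, but only as a rounding rule. No model is specified anywhere.
- Study Methods describes the design as "Population based case-control point-prevalence study".

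No section plans a prevalence ratio, a prevalence difference, a confidence interval, or a test against a ratio of 4.

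**The concern.** A test of equality can support the statement that prevalence is higher. It cannot support or refute a statement that it is four times as high. The plan has two wordings of one hypothesis, and its analysis answers only the weaker one.

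This matters because so few control cases are expected. With about one or two, a difference usually reaches significance only when the observed excess is large. A significant p-value will therefore usually come with proportions that look like 4-fold, even when the true ratio is smaller. Without an interval, the report could present 4-fold as confirmed from data that are also compatible with a ratio little above 1.

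**Working it through.** **Inputs** (from Estimated Sample Size)
- Prevalence: men 7% vs 1.0%; women 5% vs 0.5%.
- Minimum examined per group: 166 men, 206 women.
- Alpha 0.05 and power 0.80. Sidedness is not stated; two-sided is assumed.
- Expected yield at 65% participation: men 0.65 × 350 = 227.5, about 228; women 0.65 × 400 = 260.

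**1. The plan's own figures.** The formula is n = [1.96·√(2p̄(1−p̄)) + 0.8416·√(p₁(1−p₁) + p₀(1−p₀))]² / (p₁−p₀)².
- Men, p̄ = 0.04: (0.5432 + 0.2305)² / 0.06² = 166.3.
- Women, p̄ = 0.0275: (0.4533 + 0.1928)² / 0.045² = 206.1.

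Both agree with the stated 166 and 206. The null in this formula is equality, so the study is sized for higher, not for 4-fold.

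**2. Interval for the ratio at the expected yield.** SE(ln ratio) = √(1/a − 1/n + 1/b − 1/n), with a and b the expected offspring and control cases.
- Men: a = 15.96, b = 2.28, n = 228; SE = 0.702. The ratio is 7.0, 95% CI 1.8 to 27.7.
- Women: a = 13, b = 1.3, n = 260; SE = 0.916. The ratio is 10.0, 95% CI 1.7 to 60.2.

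Both lower limits are well below 4, although the assumed ratios are 7 and 10. Fractional expected counts show the likely width only. With whole counts, 16 vs 2 in men gives 8.0 (1.9 to 34.4) and 13 vs 1 in women gives 13.0 (1.7 to 98.7).

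**3. Smallest significant table.** The thresholds are the same at 166, 206, 228 and 260 per group.

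| Control cases | Offspring cases, chi-square | Offspring cases, Fisher | Observed ratio (chi-square / Fisher) |
|---|---|---|---|
| 0 | 4 | 6 | undefined |
| 1 | 7 | 8 | 7 / 8 |
| 2 | 9 | 10 | 4.5 / 5 |
| 3 | 10 | 12 | 3.3 / 4 |
| 4 | 12 | 13 | 3.0 / 3.25 |
| 5 | 14 | 15 | 2.8 / 3.0 |

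For the Fisher thresholds with 1 to 3 control cases, the log-method lower limit of the ratio is only about 1.0 to 1.15.

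**4. What a significant excess would look like.** All 2×2 tables were enumerated with binomial probabilities at the assumed control prevalence. Each cell gives chi-square / Fisher. Zero control cases count as a ratio of at least 4.

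| Group, n | True ratio | P(significant excess) | P(observed ratio ≥ 4, given significance) |
|---|---|---|---|
| Men, 166 | 2 | 0.098 / 0.029 | 0.997 / 1.000 |
| Men, 166 | 4 | 0.407 / 0.274 | 0.961 / 0.996 |
| Men, 228 | 2 | 0.123 / 0.057 | 0.973 / 0.998 |
| Men, 228 | 4 | 0.554 / 0.426 | 0.871 / 0.965 |
| Women, 206 | 2 | 0.056 / 0.007 | 1.000 / 1.000 |
| Women, 206 | 4 | 0.261 / 0.105 | 0.998 / 1.000 |
| Women, 260 | 2 | 0.078 / 0.015 | 1.000 / 1.000 |
| Women, 260 | 4 | 0.325 / 0.178 | 0.990 / 1.000 |

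**5. Zero control cases.** P(0) = (1 − p₀)ⁿ: men 0.99¹⁶⁶ = 19% and 0.99²²⁸ = 10%; women 0.995²⁰⁶ = 36% and 0.995²⁶⁰ = 27%. The crude ratio is then undefined.

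**6. Could the study show a ratio above 4?** Even at true ratios of 7 and 10, the chance that the 95% score lower limit exceeds 4 is about 2% at 166/206 and 6% to 7% at 228/260. For 80% power, n per group = (1.96 + 0.8416)² × [(1−p₁)/p₁ + (1−p₀)/p₀] / [ln(R/4)]².
- Men: 7.849 × 112.29 / 0.3132, about 2,815.
- Women: 7.849 × 218 / 0.8396, about 2,038.

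**The case against.** The strongest defence is that the aim itself only asks for a comparison of prevalence. The power section words the hypothesis as higher, the study is sized for that, and the planned tests answer it. This stands: the analysis is not wrong for that question. What remains is the conflict between the two wordings and the missing interval.

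A reader might infer that significance is possible only with an observed ratio of about 4 or more, so that a significant result looks like 4-fold whatever the truth. The plan's figures do not support this.
- Under chi-square, 10 vs 3 is significant at a ratio of 3.3. With 4 control cases both tests reach significance below 4, and at 228 men the chance of more than 3 control cases is 20%.
- The share falls to 87% in one scenario (228 men, true ratio 4, chi-square).
- The shares are conditional on significance. At a true ratio of 2, a significant excess occurs in about 3% to 12% of studies in men and 1% to 8% in women.
- Many of the counted tables have no control cases: 42% to 45% of significant results in 166 men at a true ratio of 4, and 79% to 81% in 206 women. These show no finite ratio.

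It is also fair that counts and proportions will be published, so a reader could form a ratio and interval. That does not replace a prespecified method, least of all when the control count may be zero.

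Finally, a reader might think the case-control label undermines the analysis. The groups are defined by heredity and AAA is found at the scan, so the label is inaccurate. But the plan also says point-prevalence and plans no odds ratio, so no analytic consequence follows.

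**Conclusion.** The point holds in a limited form. The 4-fold hypothesis has no analysis that addresses it, and it conflicts with the power section's wording and with the ratios of 7 and 10 used for sizing. Most significant results (about 87% to 100% at true ratios of 2 to 4) would show an observed ratio of at least 4. The interval at the expected yield, about 1.8 to 28 in men and 1.7 to 60 in women, could not separate 4-fold from much smaller ratios.

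These figures assume control prevalences of 1.0% and 0.5%, 65% participation, two-sided 0.05, uncorrected chi-square or Fisher's test, and zero-control tables counted as at least 4. A 4-fold excess is read as a ratio of 4; read as 5, it would be harder still to show. The test of higher prevalence is not in question. The change is one the sponsor should make, because it alters what the report can properly conclude.

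**What to change.** 1. In Study Objectives and Endpoints, restate the primary hypothesis as higher prevalence, consistent with the power section. Keep 4-fold, if wanted, as an expectation that is not tested.
2. In Efficacy Analyses, add for each sex the prevalence difference and the prevalence ratio (offspring vs control) with 95% confidence intervals. Name a score or exact method that remains valid with zero control cases.
3. State that a significant test is reported as higher prevalence, and that its size is described by the interval. A rule allowing a 4-fold claim only if the lower limit reaches 4 is not recommended: at this size it would be met about 2% to 7% of the time even at the assumed ratios.
4. As a minor wording note, replace case-control in Study Methods with a cross-sectional comparison of groups defined by parental AAA.

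The cost is a few lines of SAP text and two extra estimates per sex, with no new data or participants. The downside is that the report will show openly that the data cannot confirm 4-fold.
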